Tumor evaluation/staging during treatment (CT/MRI/other established methods) y						X (every 8 weeks)			Every 8 weeks for the first 24 weeks, then every 12 weeks thereafter	X			
Dosing													
Registration z		X											
Pretreatment aa		X	X	X	X								

		Treatment Period a (-3/+1 days) 1 Cycle = 14 Days								End Of Treatment/Follow-Up b			
Assessments	Screening (≤ 28 Days Prior to Enrollment)	Cycle 1	Cycle 2	Cycle 3	Cycle 4	Cycle 5	Cycle 6	Cycle 7	Until EOT	EOT/ Withdrawal Visit b	Safety Follow-up c		Survival Follow-up d
		Week 1 (Day 1)	Week 3 (Day 15)	Week 5 (Day 29)	Week 7 (Day 43)	Week 9 (Day 57)	Week 11 (Day 71)	Week 13 (Day 85)	> Week 13 (Day 85)	Within 7 Days of Decision to Discontinue	Visit 30 Days (± 5 days) After Last Tx	Phone Call 90 Days (± 5 days) After Last Tx	Every 12 Weeks (± 1 Week) After Last Tx
Avelumab administration bb		X	X	X	X	X	X	X	Q2 weeks				

AEs: adverse events; βhCG: beta-human chorionic gonadotropin; C1D1: Cycle 1 Day 1; CNS: central nervous system; CR: complete response; CT: computed tomography; ECG: electrocardiogram; eCRF: electronic Case Report Form; EOT: End of Treatment; CCI; HBV: hepatitis B virus; HCV: hepatitis C virus; IGF: insulin-like growth factor; MRI: magnetic resonance imaging; NCI-CTCAE: National Cancer Institute Common Terminology Criteria for Adverse Events; PD: progressive disease; PR: partial response; Q: every; QTc: corrected QT; RECIST 1.1: Response Evaluation Criteria in Solid Tumors version 1.1; SAE: serious adverse event; T4: free thyroxine; TSH: thyroid stimulating hormone; Tx: treatment.

- Treatment period: A time window of up to 3 days before and 1 day after the scheduled visit day (-3/+1 days) will be permitted for all treatment procedures. The biweekly, 14-day treatment schedule should be strictly adhered to, returning to the target date even if the previous visit was off schedule.

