First 36 subjects: PK blood samples in subjects < 10 kg at Baseline a,b	Predose, EOI, and 48-96 h	Predose	Predose and EOI	Predose	Predose and EOI	Predose	Predose	Predose and EOI	Predose	X	X
First 36 subjects: PK blood samples in subjects ≥ 10 kg at Baseline a,b	Predose, EOI, 3 h, and 48-96 h	Predose	Predose and EOI	Predose	Predose and EOI	Predose	Predose and EOI	Predose and EOI	Predose	X	X
PK blood samples in subjects beyond the first 36 a,b	Predose and EOI	Predose	Predose and EOI	Predose	Predose and EOI	Predose	Predose	Predose and EOI	Predose	X	X
Blood samples for ADA (immunogenicity) testing c	Predose	Predose	Predose	Predose	Predose	—	Predose	Predose	Predose	X	X

ADA: antidrug antibodies; EOI: end of infusion; EOT: End of Treatment; PK: pharmacokinetic(s).

- Predose blood samples for PK determinations will be collected from all subjects within 2 hours prior to trial treatment infusion. PK, ADA, and biomarker samples collected at the same predose time point can be used interchangeably if the dedicated sample has insufficient quantity, as the subject's parent(s)/guardian(s) will have consented to all collections and tests. PK sampling can be adjusted based on the PK data obtained from the first 3 subjects.
- Postdose samples for PK analysis will be collected at EOI and at the subsequent times indicated. The timepoint window for the EOI and 3-hour samples is ± 30 minutes. Additional PK samples will be collected during the EOT/Withdrawal Visit and at the 30-day Safety Follow-up Visit. PK samples for avelumab will be collected from all subjects in Phase I and Phase II of the study. Every effort should be made to collect PK samples as close to the protocol-prescribed time point as possible, and to record the exact time in source document. Protocol deviations will be captured if samples are not collected, or if sample collection times are not recorded.

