#### 5.1.1.1 Phase I Study Design

In the dose-finding part of the study, subjects will be enrolled in sequential cohorts of 3 to 6 subjects each; the first 3 subjects will be  $\geq 1$  year old. At least 12 subjects must be evaluable for the primary analysis. Phase I will be completed when at least 12 DLT-evaluable subjects have been treated at a dose level confirmed to be safe. Phase II will then begin.

The starting dose will be the same as recommended dose in adults, 10 mg/kg avelumab administered intravenously (iv) once every 2 weeks, which is based on modeling and simulation results using adult PK data from ongoing avelumab studies as described in Section 5.2. Avelumab will be administered until confirmed progression, death, unacceptable toxicity, or any criterion for withdrawal occurs. In Phase I, the DLT observation period is defined as a 28-day period (2 cycles) beginning with the first avelumab administration.

The first cohort of 3 to 6 subjects will be enrolled at the starting dose level of 10 mg/kg (DL1). Based on the number of subjects experiencing DLTs at the completion of the first cohort, the dose for the next cohort of subjects can be kept the same or modified.

- If DL1 is confirmed as safe, this dose will be selected as RP2D if it provides adequate exposure in children compared with adults.
- If exposure is not adequate (when compared with adult population PK [PopPK]-simulated values for median and distribution of exposure [ $C_{max}$ , AUC, and  $C_{trough}$ ]), a decision can be made to escalate to a dose level up to 20 mg/kg (DL2).
- If at any point the modified toxicity probability interval (mTPI) results indicate a dose de-escalation is warranted, the next subjects will be enrolled at lower dose level of 3 mg/kg every 2 weeks (DL -1). Dose re-escalation can be permitted based on the mTPI results as long as the current dose level has not been determined to have exceeded the MTD. The MTD estimate is the highest dose tested of avelumab associated with the occurrence of DLTs within the first 2 cycles of treatment in < 33% of subjects, provided that a higher dose level of avelumab was tested and had an associated DLT rate  $\geq$  33%.

Subjects will return to the clinic at regular intervals for assessments (see Section 7.1 and Table 1).

Avelumab treatment will continue until:

- PD (see Section 5.5.1) or death
- Unacceptable toxicity
- Any criterion for withdrawal from the trial or trial treatment is fulfilled (see Section 5.5).

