#### 5.1.3.2 Adverse Drug Reactions Requiring Avelumab Treatment Discontinuation or Modifications

The following adverse drug reactions (ADRs; for definition, see Section 7.4.1.1) require permanent treatment discontinuation of avelumab:

- Any Grade 4 ADR, except for the following:
  - Grade 4 lipase or amylase abnormality that is not associated with clinical manifestations of pancreatitis. The Medical Monitor must be consulted for such lipase and amylase abnormalities.
  - Grade 4 neutropenia of  $\leq 7$  days in duration
  - Grade 4 thrombocytopenia without bleeding
  - Other single laboratory values out of normal range that do not have any clinical correlate and resolve to baseline within 7 days with adequate medical management.
- Any Grade 3 ADR except for any of the following:
  - Transient ( $\leq 72$  hours) Grade 3 flu-like symptoms or fever, which are controlled with medical management
  - Transient ( $\leq 72$  hours) Grade 3 fatigue, local reactions, headache, nausea, or emesis that resolve to Grade  $\leq 1$  or baseline with appropriate medical management
  - Grade 3 diarrhea or Grade 3 skin toxicity that resolves to Grade  $\leq 1$  in less than 7 days after medical management (eg, immunosuppressant treatment) has been initiated
  - Grade 3 lipase or amylase abnormality that is not associated with clinical manifestations of pancreatitis. The Medical Monitor must be consulted for such lipase and amylase abnormalities.

- Other single laboratory values out of normal range that do not have any clinical correlate
- Tumor flare phenomenon defined as local pain, irritation, or rash localized at sites of known or suspected tumor
- Any Grade 2 ADR should be managed as follows:
  - Infusion should not be given in case of ongoing Grade 2 ADR on the day of trial treatment administration.
  - Treatment can be resumed according to original schedule once ADR resolves to Grade  $\leq 1$ . Up to 2 subsequent study drug doses may be omitted. If more than 2 doses are skipped, treatment may be resumed after consultation with the study Medical Monitor.

See the guidelines for handling infusion-related reactions (Section 6.5.5.1), severe hypersensitivity reactions and flu-like symptoms (Section 6.5.5.2), and irAEs (Section 6.5.5.3).

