16.1.1 PK Concentration Data

Pre-dose samples that occur before the first drug administration will be assigned a time of 0 hours, as if the sample had been taken simultaneously with the study drug administration.

Values below the lower limit of quantification of the assay (LLOQ) will be taken as zero for summary statistics of PK concentration data. Missing concentrations (e.g. no sample, insufficient sample volume for analysis, no result or result not valid) will be reported and used generally as "N.R."

PK concentrations which are questionable due to a protocol deviation (as defined in the CTP), documented handling error or analytical error (as documented in the bioanalytical report) may be excluded from the PK analysis if agreed upon prior to performing a statistical analyses. In this case the rationale for exclusion must be provided in the Clinical Study Report (CSR). Any other PK concentrations that appear implausible to the Pharmacokineticist/PKPD Data Analyst must not be excluded from the analysis. Any implausible data will be documented in the Clinical Study Report (CSR).

Based on Table 2 (Schedule of Assessments – Pharmacokinetic and Antidrug Antibody Sampling) of the CSP, the timepoint window for the EOI and 3-hour samples is ± 30 minutes. Samples that are collected outside the specified time windows will be included in the PK parameter estimation (NCA) but will be excluded from the concentration summary and mean concentration plots.

Serum avelumab PK concentration data will be listed and summarized by dose level, day and nominal time using standard descriptive statistics including the number of non-missing observations (N), arithmetic mean (Mean), standard deviation (SD), coefficient of variation (CV%), minimum (Min), median (Median), and maximum (Max).

Individual concentration-time profiles showing all subjects by dose level will be created using the actual time points and the numeric concentration data. Arithmetic mean concentration-time profiles by dose level/cohort will be provided using scheduled (nominal) time points and the numeric concentration data. All concentration-time plots for PK data will be presented both on a linear and on a semi-logarithmic scale. Mean plots will include SD error bars when plotted on a linear scale.

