16.1.2 Estimation of Individual PK Parameters

Population: PK Analysis Set

Pharmacokinetic parameters will be calculated by the PK/PD Processing Group of QPD, Merck, Darmstadt, Germany, or by a CRO selected by the Sponsor, using standard non-compartmental methods and the actual administered dose. PK parameters will be calculated using the actual

elapsed time since dosing, given with a precision of 14 significant digits or the SAS format Best12. In cases where the actual sampling time is missing, calculations will be performed using the scheduled time. Otherwise, there will be no further imputation of missing data.

Non-compartmental computation of pharmacokinetic parameters will be performed using the computer program PPD[®] version 6.3, or higher PPD[®].

The statistical software SAS[®] (Statistical Analysis System, SAS-Institute, Cary NC, USA, windows version 9.1 or higher) may be used to produce tables, listings and figures and in the calculation of PK Parameters if appropriate.

PK parameters will be listed and summarized by dose level, cycle, and day (if applicable) using standard descriptive statistics.

All statistical analyses and descriptive summaries of pharmacokinetic data will be performed on the PK Analysis Set. The mean concentration-time profiles and PK parameter plots will be plotted using the PK Analysis Set and the individual participant concentration-time profiles will use the Safety Analysis Set. Any PK concentrations excluded from the PK analysis set will be listed and flagged.

The following avelumab PK parameters will be calculated where appropriate:

Symbol	Definition
AUC_{τ}	The area under the concentration-time curve (AUC) over the dosing interval (τ) from $T_1=0$ h to $T_2=336$ h (i.e. 14 days). Calculated using the mixed log linear trapezoidal rule (linear up, log down). For single dose, AUC_{τ} is calculated as a partial area with the defined time range. In multiple dose profiles AUC_{τ} is calculated at steady state from one pre-dose time point to the dosing interval time. In cases where the actual observation time is not equal to the scheduled observation time AUC_{τ} will be calculated based on the estimated concentration at τ hours, and not the concentration at the actual observation time. This parameter is calculated following dosing in Cycle 1, Day 1 only. Unit = $\mu\text{g}\cdot\text{h}/\text{mL}$.

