C_{trough}	The concentration observed immediately before next dosing (corresponding to pre-dose or trough concentration for multiple dosing). Unit = $\mu\text{g}/\text{mL}$.
$t_{1/2}$	Apparent terminal half-life. $t_{1/2} = \ln(2)/\lambda_z$. This parameter is calculated following dosing in Cycle 1, Day 1 only. Unit = h.
V_z	The apparent volume of distribution during the terminal phase following intravenous administration. $V_z = Dose/(AUC_{0-\infty}*\lambda_z)$ following dosing in Cycle 1, Day 1 only. Unit = L.
λ_z	Terminal first order (elimination) rate constant. Determined from the terminal slope of the log-transformed concentration curve using linear regression on terminal data points of the curve. This parameter is calculated following dosing in Cycle 1, Day 1 only. Unit = 1/h.

The following PK parameters will be calculated for diagnostic purposes and listed, but will not be summarized:

- The time interval (h) of the log-linear regression ($\lambda_{z\ low}$, $\lambda_{z\ upp}$) to determine λ_z .
- Number of data points (N_λ) included in the log-linear regression analysis to determine λ_z .
- Goodness of fit statistic (Rsqr,adj) for calculation of λ_z .

The regression analysis should contain data from at least 3 different time points in the terminal phase consistent with the assessment of a straight line on the log-transformed scale. PPD best fit methodology will be used as standard. The last quantifiable concentration should always be included in the regression analysis, while any concentrations <LLOQ which occur after the last quantifiable data point should not be used.

The coefficient of determination (Rsqr,adj) should be ≥ 0.8000 and the observation period over which the regression line is estimated should be at least twofold the resulting $t_{1/2}$ itself. If these criteria are not met, then the rate constants and all derived parameters (e.g. CL, and V_z etc.) will be included in the parameter outputs and descriptive statistics but will be flagged and discussed appropriately. Any flags should be included in the study specific SDTM.

Partial areas AUC_τ should be calculated using the scheduled dosing interval, as defined in the CTP. The actual dosing interval calculated from CRF time data should not be used. The following rules apply when calculating the partial area AUC_τ within the observed time interval from T_1 to T_2 :

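### Ctrough has no limit on time since the previous dose, so troughs drawn after omitted doses bias its summaries downward

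*SAP*

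**What the plan says.** **Definition.** The parameter table in SAP 16.1.2 defines Ctrough as "The concentration observed immediately before next dosing (corresponding to pre-dose or trough concentration for multiple dosing". Values are summarised by dose level and cycle. SAP 16.1.2.1 adds the geometric mean with its 95% CI, and SAP 16.1.2.2 adds arithmetic mean trough plots. Both the summaries and the plots are also split by weight (below 10 kg, or 10 kg and above).

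**Sampling windows.** Protocol Table 2, footnote a, states: "Predose blood samples for PK determinations will be collected from all subjects within 2 hours prior to trial treatment infusion". This window is tied to the coming dose. SAP 16.1.1 mentions only that "the timepoint window for the EOI and 3-hour samples is ± 30 minutes". It drops out-of-window samples from concentration summaries and mean concentration plots but keeps them for parameter estimation.

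**Exclusions.** SAP 16.1.1 allows a concentration to be excluded for a protocol deviation, a handling error or an analytical error. Other values that look implausible have to stay in.

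**Omitted doses.** Protocol 5.1.3.2, on Grade 2 reactions: "Up to 2 subsequent study drug doses may be omitted. If more than 2 doses are skipped, treatment may be resumed after consultation" with the Medical Monitor. Dosing then continues on the planned schedule.

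**Use.** Protocol 5.1.1.1 opens the route to a higher dose level as follows: "If exposure is not adequate (when compared with adult population PK [PopPK]-simulated values for median and distribution of exposure", and names Cmax, AUC and Ctrough as the measures.

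**The concern.** A trough is interpretable only relative to the interval that it closes. Here the interval is left open, and the protocol itself creates long ones. An omission under 5.1.3.2 complies with the protocol, so the exclusion for deviations does not catch the resulting sample.

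The SAP deals with the same issue for another parameter. AUC over the dosing interval is fixed at 336 h, and when the actual time differs from the scheduled time it uses the estimated concentration at 336 h. Ctrough has no counterpart.

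At stake is the description of multiple-dose exposure. Cmax and AUC are computed after Cycle 1 Day 1 only, so of the three measures named for the adult comparison, Ctrough is the only one that the SAP follows beyond Cycle 1. The contamination is also informative: doses are omitted because of adverse reactions, so subjects with toxicity would appear to have low exposure.

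**Working it through.** **Intervals, from the documents**

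- Dosing interval: 14 days × 24 = 336 h, which agrees with the SAP.
- Visit window (Protocol Table 1, footnote on the treatment period): "A time window of up to 3 days before and 1 day after the scheduled visit day". It applies to each visit, so both ends of an interval can move.

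| Doses omitted | Nominal gap (days) | Gap between in-window doses (days) |
|---|---|---|
| 0 | 14 | 14 − 3 − 1 = 10 to 14 + 3 + 1 = 18 |
| 1 | 28 | 24 to 32 |
| 2 | 42 | 38 to 46 |

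The ranges do not overlap, so elapsed time alone separates regular troughs from those after an omission.

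**Effect on one value**

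The half-life is an assumption, as the documents give none. With log-linear one-compartment decay at steady state, the trough after one omitted dose relative to the regular trough is r = 2^(−14/t½). After two it is 2^(−28/t½). For the Cycle 3 trough with Cycle 2 omitted it is r/(1 + r).

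| Assumed t½ (days) | One omitted | Two omitted | Cycle 3, Cycle 2 omitted |
|---|---|---|---|
| 4 | 0.088 | 0.008 | 0.081 |
| 6 | 0.198 | 0.039 | 0.166 |
| 8 | 0.297 | 0.088 | 0.229 |
| 14 | 0.500 | 0.250 | 0.333 |

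**Effect on the group summary**

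Suppose m of n subjects are affected by one omission each. The geometric mean is multiplied by r^(m/n) and the arithmetic mean by 1 − (m/n)(1 − r). The median was simulated with lognormal values and an assumed log-SD of 0.5. The group size n = 12 is the protocol's minimum number of DLT-evaluable subjects; m is illustrative. Ranges below run from t½ = 4 to 8 days.

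| Affected of 12 | Geometric mean × | Arithmetic mean × | Median × |
|---|---|---|---|
| 1 | 0.817 to 0.904 | 0.924 to 0.941 | about 0.97 |
| 2 | 0.667 to 0.817 | 0.848 to 0.883 | about 0.90 |
| 3 | 0.545 to 0.738 | 0.772 to 0.824 | 0.83 to 0.84 |

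Example for one of 12 at t½ = 8 days: 0.297^(1/12) = 0.904, a fall of 10%. At 4 days: 0.088^(1/12) = 0.817, a fall of 18%. At 14 days the factor is 0.944, so the effect is smaller but still downward. In a group of 6, such as a small weight stratum or a late visit, one affected value multiplies the geometric mean by 0.667 to 0.817 and the median by about 0.92.

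**The case against.** The tempting stronger reading is that this definition lowers the exposure measure used to choose the recommended Phase II dose, and so favours a false finding of inadequate exposure. The documents do not support it, for three reasons:

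- **Timing.** The Safety Monitoring Committee decides on dose during Phase I, with final adjudication by the sponsor (Protocol 2.3). PK from the first 3 subjects at the starting dose is evaluated before anyone else is dosed (Protocol 5.1.1.1.1). The SAP summaries follow database lock (SAP section 6). No text ties the committee's comparison to them.
- **One measure of three.** Cmax and AUC come from Cycle 1 Day 1, so later omissions cannot touch them.
- **Statistic.** The protocol compares the median and the distribution. The median falls only about 3% with one of 12 affected.

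Other points narrow the problem without removing it:

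- Predose PK is taken at Cycles 1, 2, 3, 5, 7, 8, 13, 19, 25 and every 6 cycles after that. If cycles are numbered by calendar, the long gap reaches a sampled trough only when the dose just before that cycle was omitted.
- The PK Analysis Set (SAP 8.2) leaves out subjects with important events that affect PK. The term is undefined, and the rule removes whole subjects, valid troughs included.
- Dose delays and individual values are listed, so affected values could be traced. A listing does not correct a mean.

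**Conclusion.** The gap is real and its direction is certain: applied as written, the SAP pools troughs after omitted doses with 14-day troughs, and the Ctrough summaries and mean trough plots come out low. For one omitted dose in one of 12 subjects, the geometric mean falls 10% to 18%, the arithmetic mean 6% to 8%, and the median about 3%. These sizes rest on an assumed half-life of 4 to 8 days, log-linear decay, an assumed log-SD of 0.5 for the median, and an illustrative number affected; the documents do not give the share of subjects with omitted doses. The consequence is a biased description of a secondary PK endpoint intended for the study report, and possibly for submissions or manuscripts (SAP section 4). It should not be read as evidence that the dose selection was wrong.

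**What to change.** In SAP 16.1.1 and 16.1.2, include a predose value in the Ctrough summaries and mean trough plots only if the time since the previous infusion is 10 to 18 days, the range possible between consecutive in-window doses. List and flag all other predose values with their actual elapsed time, and keep them for the population PK analysis.

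The −3/+1 days should not be applied directly to the interval. That would give 11 to 15 days and discard compliant troughs: a dose given 3 days early, followed by a return to the target date, yields 17 days.

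It would also help to define the events affecting PK in SAP 8.2, and to state whether the committee's exposure comparison used the same trough rule.

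The cost is some SAP wording and one date check on data already collected. The downside is a few fewer values per visit. The 10-to-18-day range still admits ordinary timing variation (a factor of 1.41 to 0.71 relative to day 14 at an assumed half-life of 8 days), but that variation runs in both directions and arises from compliant visits.

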16.1.2.1 Presentation of PK Parameter data

PK parameter data will be descriptively summarized using: N, Mean, SD, CV%, Min, Median, Max, geometric mean (GeoMean), the geometric coefficient of variation (GeoCV) and the 95%

confidence interval for the GeoMean (lower confidence interval (LCI) 95% GeoMean, upper confidence interval (UCI) 95% GeoMean).

PK parameters C_{max} , C_{EOI} and C_{trough} will be reported with the same precision as the source data. All other PK parameters will be reported to 3 significant figures. In export datasets, as well as in the SDTM PP domain, PK parameters will be provided with full precision, and will not be rounded. Descriptive statistics of PK parameter data will be calculated using full precision values, and rounded for reporting purposes only.

The following conventions will be applied when reporting descriptive statistics of PK parameter data:

Mean, Min, Median, Max, GeoMean, 95% CI:	3 significant digits
SD:	4 significant digits
CV%, GeoCV%:	1 decimal place

